15.1.3. PRIMARY ANALYSIS OF PRIMARY EFFICACY VARIABLE

The primary endpoint will be performed for the ITT population primarily using a linear mixed model with a fixed effect term for treatment, centre as a random effect and the baseline RDQ GERD dimension score as a covariate. The primary analysis is to test the null hypothesis that there is no difference between treatment, least square means (with 95% CI) corresponding to the two treatments will be presented. Descriptive statistics will also be presented for the primary endpoint by treatment.

The following SAS core code will be used:

```
proc mixed data=XXX method=REML;
  class treatment center;
  model chg = base treatment / DDFM=KR;
  random center;
  lsmeans treatment/diff cl;
run;
```

15.1.4. SENSITIVITY ANALYSIS OF PRIMARY EFFICACY VARIABLE

A sensitivity analysis will be conducted on the primary endpoint using the PP population.

15.1.5. EXPLORATORY ANALYSIS OF PRIMARY EFFICACY VARIABLE

Two additional separate exploratory mixed models will be conducted identical to those stated above but with additional interaction terms for the treatment by centre interaction (random effect) and treatment by baseline covariate interaction respectively.

15.1.6. SUBGROUP ANALYSIS OF PRIMARY EFFICACY VARIABLE

The analysis will be repeated within each of the subgroups separately as indicated below:

GERD status: Erosive vs Non-erosive.

15.2. SECONDARY EFFICACY

15.2.1 SECONDARY EFFICACY VARIABLES

The key secondary endpoint is:

Document: Reckitt Benckiser GA1210 Statistical Analysis Plan

Author: [REDACTED]

Version Number:

2.0

Version Date:

29Jul2014

Template No: CS_TP_BS016 – Revision 3

Reference: CS_WI_BS005

Effective Date: 01May2012

Page 16 of 23

-
- Change from baseline in RDQ scores for dyspepsia dimension

Other secondary endpoints are:

- Overall treatment evaluation (OTE) as a measure for patient's responsiveness/satisfaction;
- Change from baseline in RDQ scores for heartburn dimension;
- Change from baseline in RDQ scores for regurgitation dimension.

The secondary efficacy analyses will be performed for the ITT population.

Refer to Appendix B for RDQ scoring instructions for deriving the RDQ symptom scores for the dyspepsia, heartburn and regurgitation dimension.

The two OTE responses are collected on the "Overall Treatment Evaluation" form in eCRF as responses to questions 1) thinking over the last 7 days and the medication you received, how would you rate the change in your symptoms; and 2) how important was the change in the symptoms to you.

15.2.2 MISSING DATA METHODS FOR SECONDARY EFFICACY VARIABLES

For those patients that do not return for Visit 3 because of confirmed poor efficacy from the treatment between Day 1 and Day 6, all efficacy data concerning RDQ scores at Visit 3 will be imputed as no change from the day 0 values (BOCF) if Early Termination visit is missing. If there is missing data for a patient in the RDQ questionnaire at an occasion and the missing data is less than 50% of the item scores within a dimension, the missing items will be imputed using the mean score of the non-missing item scores. If more than 50% of the item scores are missing, no imputation will be performed and the dimension score will be excluded from the analysis.

15.2.3 ANALYSES OF SECONDARY EFFICACY VARIABLES

The analysis methods for the key secondary endpoint will be identically to those described for the primary endpoint in 15.1.3, 15.1.4 and 15.1.5 except that the included covariate will be the baseline RDQ score for the relevant dimension.

The difference in the two OTE responses will be compared between treatment groups using a Wilcoxon Rank Sum Test stratified by centre.

The following SAS core code will be used:

```
proc freq data=XXX;
  tables center*treatment*ote_resp/cmh2 scores=modridit ;
  run;
```

The second OTE response (i.e., how important was the change in symptoms) will also be examined in the subgroup of patients who have reported an improvement in the first OTE response.

The change scores in frequency and intensity for each dimension, i.e., the 12 items asked on the RDQ questionnaire, will be compared between treatment groups using a Wilcoxon Rank Sum Test stratified by centre.

The analysis methods for the other two secondary endpoints (heartburn and regurgitation dimensions) will be

Document: Reckitt Benckiser GA1210 Statistical Analysis Plan

Author: [REDACTED]

Version Number:

2.0

Version Date:

29Jul2014

Template No: CS_TP_BS016 – Revision 3

Reference: CS_WI_BS005

Effective Date: 01May2012

Page 17 of 23

identical to those described for the primary endpoint in 15.1.3 and 15.1.4 except that the included covariate will be the baseline RDQ score for the relevant dimension.

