14.4.3 Statistical Methods for Efficacy Analyses

All statistical tests performed will be 2-tailed with significance assessed at the 5% significance level. The null hypothesis at all times will be the equality of the treatments being compared.

Normality assumptions will be evaluated by an examination of the residual plots. Depending on the degree of departure from these assumptions, an alternate nonparametric approach may be used for supportive purposes.

The primary endpoint (change in RDQ GERD dimension score) will be analysed using an analysis of covariance (ANCOVA) model with a fixed effect term for treatment, centre as a random effect and the day 0 RDQ GERD dimension score as a covariate. Treatment group differences will be estimated using the least square means and presented with 95% confidence intervals and p-values to make inferences.

The change in symptom score for each dimension separately will be analysed identically to the primary endpoint although the included covariate will be the relevant dimension day 0 score rather than the GERD dimension score.

To preserve the type 1 error rate of 5% for the key secondary endpoint (change from day 0 in RDQ scores for dyspepsia dimension), a closed testing procedure will be applied. A significant comparison at the 5% level ($p<0.05$) for this key secondary endpoint will only be deemed as confirmatory evidence if the primary endpoint is also significant at the 5% significance level ($p<0.05$). All other secondary endpoints and/or any further sensitivity or alternate analyses for the primary and key secondary endpoint will serve as supportive evidence only and therefore no further adjustment for multiple comparisons will be made.

For the primary and key secondary endpoint, two additional separate exploratory ANOVA models will be conducted identical to those stated above but with one additional interaction term for the treatment by centre interaction (random effect) and treatment by baseline covariate interaction respectively.

The change scores in frequency and intensity for each dimension as well as the two OTE responses will be compared between treatments using a Wilcoxon Rank Sum Test stratified by centre.

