7.2. BASELINE

Unless otherwise specified, baseline value refers to the tests or measurements recorded at Visit 1, screening

Document:	Reckitt Benckiser GA1210 Statistical Analysis Plan		
Author:	[REDACTED]	Version Number:	2.0

Template No: CS_TP_BS016 – Revision 3

Reference: CS_WI_BS005

Effective Date: 01May2012

Version Date:

29Jul2014

Page 10 of 23

visit. If a particular test or measurement was repeated after Visit 1, screening visit, then the baseline value is defined as the last non-missing measurement taken prior to Visit 2, Day 0 (including unscheduled assessments). Baseline for RDQ scores are collected on Day 0. In the case where the last non-missing measurement and the reference start date coincide, that measurement will be considered pre-baseline, but Adverse Events (AEs) and medications commencing on the reference start date will be considered post-baseline.

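### The 12 RDQ item comparisons test raw change without the item's Day 0 score: valid and supportive only, but they give up precision by an amount the documents cannot fix

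*SAP*

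**What the plan says.** - **Items.** SAP 15.2.3: "The change scores in frequency and intensity for each dimension, i.e., the 12 items asked on the RDQ questionnaire, will be compared between treatment groups". The method named there is a centre-stratified Wilcoxon test. Protocol 14.4.3 has the matching sentence: "The change scores in frequency and intensity for each dimension as well as the two OTE responses will be compared between treatments". It names the same method, and the synopsis (3.11) repeats it. Neither document uses the item's Day 0 score as covariate or stratum, and no baseline-adjusted item analysis appears elsewhere.
- **Dimensions.** The primary model in SAP 15.1.3 includes "the baseline RDQ GERD dimension score as a covariate", coded as "model chg = base treatment / DDFM=KR". The dyspepsia, heartburn and regurgitation scores follow the same model, "except that the included covariate will be the baseline RDQ score for the relevant dimension" (SAP 15.2.3).
- **Baseline.** SAP 7.2: "Baseline for RDQ scores are collected on Day 0". The schedule in protocol 11.2 has the RDQ completed at Visit 2.
- **Scoring.** SAP Appendix 2 scores each item 0 to 5 and averages frequency and intensity items together within each dimension.
- **Role.** The item comparisons are not among the secondary endpoints listed in SAP 15.2.1. They lie outside the closed test of SAP 8.4, which leaves only the primary and key secondary endpoints as confirmatory. No power is stated for them.

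**The concern.** The same questionnaire is handled in two ways and neither document says why. On a 0 to 5 item, the possible change depends on where the patient starts: a patient at 0 cannot improve, and a patient at 5 can fall by up to 5. Ranking raw change therefore brings Day 0 spread, which has nothing to do with treatment, into the outcome. Randomisation keeps the test valid, but it can be less sensitive than an analysis that uses the Day 0 score.

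Because the dimension scores mix frequency with intensity, the item tests are the only place where the plan can show whether treatment changes how often a symptom occurs or how bad it is. A less sensitive test there may miss an item effect that the same data would show after adjustment.

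**Working it through.** **1. The plan's own figure.** Protocol 14.1 assumes effect size 0.2 for dyspepsia, two-sided 5%, 90% power and a two-group t-test. The noncentral t solution is 526.33, so 527 per arm and 2 × 527 = 1054, as stated. The pilot effect sizes also reproduce: 0.61 ÷ 0.9735 = 0.627 and 0.43 ÷ 1.121 = 0.384. These rest on residual SDs after baseline adjustment. The documents give no Day 0 to Visit 3 correlation and no separate Day 0 and Visit 3 SDs, for items or for dimensions.

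**2. Formula.** Let r be the Day 0 to Visit 3 correlation and k = SD(Day 0)/SD(Visit 3). In units of the Visit 3 variance, the baseline-adjusted outcome has variance 1 − r² and raw change has variance 1 + k² − 2rk. The efficiency of raw change relative to adjustment is

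E = (1 − r²)/(1 + k² − 2rk),

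which is (1 + r)/2 when k = 1. It reaches 1 only when the slope of Visit 3 on Day 0, r/k, equals 1. The formula is for a continuous score analysed linearly, so for ranked 0 to 5 items it is a guide.

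**3. Numbers (r and k assumed).** Each cell gives E and then the power of raw change at 527 per arm if the adjusted analysis has effect size 0.2 and so 90% power. That effect size is borrowed from the dyspepsia dimension for illustration.

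| k | r = 0.3 | r = 0.5 | r = 0.7 |
|---|---|---|---|
| 0.7 | 0.85; power 84.9% | 0.95; power 88.6% | 1.00; power 90.1% |
| 1.0 | 0.65; power 74.5% | 0.75; power 80.3% | 0.85; power 84.9% |
| 1.3 | 0.48; power 61.1% | 0.54; power 66.5% | 0.59; power 70.0% |

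Lowest cell (k = 1.3, r = 0.3): 1 − r² = 0.91 and 1 + k² − 2rk = 1.91, so E = 0.91 ÷ 1.91 = 0.476. Highest cell (k = 0.7, r = 0.7): both terms are 0.51, so E = 1. At k = 1, raw change would need 1054 ÷ 0.65 = 1622 patients at r = 0.3, then 1054 ÷ 0.75 = 1406 at r = 0.5 and 1054 ÷ 0.85 = 1240 at r = 0.7, to match the adjusted analysis with 1054.

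**4. Simulation with ordinal items and centre effects.** Settings: 34 centres of 31 patients (1054), latent shift 0.2 SD, centre effects with SD 0.3, 600 runs per setting. Normal latent scores were cut at −1.2; −0.8; −0.3; 0.3; 1.0 (Day 0) and −0.5; 0; 0.4; 0.9; 1.6 (Visit 3), all assumed. The stratified Wilcoxon test on change was compared with a centre-stratified rank analysis of covariance.

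| latent r | Wilcoxon on change | Rank ANCOVA |
|---|---|---|
| 0.3 | 67% | 87% |
| 0.5 | 79% | 92% |
| 0.7 | 91% | 97% |

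With no treatment effect, at four values of latent r from 0.2 to 0.7, rejection was 3.8% to 4.8% for change and 4.3% to 5.8% for rank ANCOVA. The Monte Carlo standard error is about √(0.05 × 0.95 ÷ 600) = 0.9 points.

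**5. Dependence on the Day 0 distribution.** With an assumed compressed baseline (3% zeros at Day 0, k about 0.69; 1040 patients in 26 centres, 250 runs, Monte Carlo error 2 to 3 points), power was 84% v 87%, 88% v 92% and 96% v 96% at r = 0.3, 0.5 and 0.6. With 25% zeros at Day 0 and 40% at Visit 3, it was 57% v 81% at r = 0.3. A further simulation with unequal centre sizes gave gaps of 11 to 28 points with many Day 0 zeros and 1 to 8 points with a compressed baseline. Rank ANCOVA was never less powerful there, and its size stayed near 5%.

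**The case against.** The strongest reply is that this is a choice between two valid methods in analyses on which nothing turns. A stratified Wilcoxon test on change is conventional and tests the quantity the protocol names. All 12 items already enter baseline-adjusted dimension scores. Rank analysis of covariance tests residual ranks of the Visit 3 score, so it moves away from the named change score and gives no estimate in score units.

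The loss may also be small. Protocol 10.1 requires troublesome heartburn and/or regurgitation on at least five days of the week before screening. On the frequency scale in protocol 11.4.1.2, five or more days score 4 or 5. This tends to compress Day 0 scores for qualifying symptoms, pushing k below 1, where the loss is smallest.

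Most of this stands. The consequence is minor, and the size will differ by item: the and/or wording and the optional status of dyspepsia mean that other items may have many Day 0 zeros. What does not stand is that the methods are interchangeable. The formula never favours raw change, the simulations showed no power advantage for it, and the documents give no reason for treating items differently from dimensions.

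A reader might infer a loss equivalent to 20% to 35% of patients. That follows from (1 + r)/2 with r = 0.6 and 0.3, but only if the Day 0 and Visit 3 SDs are equal. The documents give neither SD, so the figure is one slice of an unknown range.

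**Conclusion.** The point holds as a minor improvement to a supportive analysis. The item tests leave out a baseline that is already collected and that every dimension analysis uses. Under assumed r of 0.3 to 0.7 and k of 0.7 to 1.3, raw change keeps about 48% to 100% of the information of an adjusted analysis (65% to 85% if k = 1). The loss is smallest for items whose Day 0 scores the entry criteria compress. No single figure can be drawn from the documents.

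Two stronger readings are not supported. One is that the item test is biased or has inflated error: it is valid under randomisation, and simulated size was near 5%. The other is that the trial's conclusions are weakened: the primary and key secondary analyses are baseline-adjusted, the 1054 reproduces, and the item tests are outside the closed procedure.

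**What to change.** In SAP 15.2.3, for each of the 12 items:

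1. Among patients with both values, compute standardised within-centre ranks (rank divided by centre size plus one, mean ranks for ties) of the Visit 3 and Day 0 scores.
2. Regress the Visit 3 ranks on the Day 0 ranks with one slope pooled over centres, and keep the residuals.
3. Compare the residuals between treatments with the centre-stratified CMH row-mean-score test using `scores=table`. Copying the OTE call with `scores=modridit` would rank the residuals again.

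Keep descriptive summaries of raw item change, leave the OTE test as it is, and record the departure from protocol 14.4.3 in the SAP, as protocol section 14 provides.

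The cost is SAP wording, a deviation entry, and one ranking and regression step per item. The SAP gives code only for OTE, so item code has to be written anyway. There are no new data and no effect on the confirmatory tests. The small downside is that the test statistic is no longer on the raw change score.

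The change form dated 01 September 2014 at the end of the SAP shows that unblinded output had been reviewed by then. If adopted after unblinding, the analysis should be labelled a post-hoc supplement beside the planned test.

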15.2.4 SENSITIVITY ANALYSES OF SECONDARY EFFICACY VARIABLES

Sensitivity analyses will be conducted on the secondary endpoints using the PP population.

15.2.5 EXPLORATORY ANALYSIS OF KEY SECONDARY EFFICACY VARIABLES

Two additional separate exploratory mixed models will be conducted identical to those stated above but with additional interaction terms for the treatment by centre interaction (random effect) and treatment by baseline covariate interaction respectively.

16 SAFETY OUTCOMES

All outputs for safety outcomes will be based on the Safety population.

16.1 ADVERSE EVENTS

Adverse Events (AEs) will be coded using MedDRA version 17.0. For an individual patient, only adverse events commencing after first dose of IMP and no later than last dose of IMP+1day will be included in the AE and serious adverse event (SAE) summaries. AEs that began prior to the first dose of IMP or more than one day after the final dose of IMP will not be included in the analysis. Where an AE start date is partially or completely missing, and it is unclear using partial dates as to whether the AE is treatment-emergent, it will be assumed that it is.

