9.5 Study Duration

It is estimated that it will take 9 months to recruit the required number of patients.

The duration of each patient's participation in the study will be a maximum of 17 days (from screening visit to end of treatment visit) and involve 3 visits.

Patients can enter the study, if eligible, as soon as all screening results are available following informed consent at Visit 1. A maximum of 7 days will be allowed to screen a patient at Visit 1. If eligible, the patient will be randomised and will commence the 7-day treatment period at Visit 2 (Day 0).

The patients will be randomised to receive either Compound Sodium Alginate Double Action Chewable Tablets or matching placebo tablets for 7 days. Visit 3, the End of study visit, will occur on Day 8 (between Day 7 and Day 10).

The anticipated overall duration of study conduct is expected to be approximately one year.

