7. GENERAL CONSIDERATIONS

7.1. REFERENCE START DATE AND STUDY DAY

Study Day will be calculated from the reference start date, and will be used to show start/stop day of assessments and events.

Reference start date (Day 0) is defined as the day of randomisation.

- Study Day = (date of event – reference start date).

In the situation where the event date is partial or missing, Study Day, and any corresponding durations will appear partial or missing in the listings.

Randomization date will be considered as the same date of randomization visit, that is, visit 2.

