14.1. DERIVATIONS

The date of first treatment administration will be the day after "date of dispense" on the eCRF "Drug Dispense" at Visit 2. The date of last treatment administration will be the day before the date of Visit 3 or Early Termination; for patients who do not have a Visit 3 or Early Termination date, the drug return date on the eCRF "Drug Return" will be used. Time on treatment in days will be derived from the following formula:

Document:	Reckitt Benckiser GA1210 Statistical Analysis Plan	Version Number:	2.0
Author:	[REDACTED]	Version Date:	29Jul2014

Template No: CS_TP_BS016 – Revision 3

Reference: CS_WI_BS005

Effective Date: 01May2012

Page 14 of 23

Time on treatment (days) = (date of Visit 3 or Early Termination or drug return date-1) – (date of dispense at Visit 2 +1) + 1

Compliance with study treatment is based on the drug accountability data recorded on the eCFR “Drug Dispense” and “Drug Return” forms and will be calculated as the number of tablets taken (total dispensed – total returned) divided by the prescribed number of tablets expressed as a percentage, see calculations below:

Θ = Prescribed number of tablets required to be taken per day, i.e., 8 tablets in this study.

$$\text{Compliance (\%)} = \frac{[\text{N of tablets dispensed at Visit2}]-[\text{N of tablets returned at Visit3 or Early Termination}]}{\text{Time treatment}(days)*\Theta} \times 100$$

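### SAP 16.1 states two different start rules for counted AEs; run on dates, the first one drops events that begin on the first dosing day

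*SAP*

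**What the plan says.** SAP 16.1 (Adverse Events) sets the window for the AE and SAE summaries in two consecutive sentences. The first is an inclusion rule: "only adverse events commencing after first dose of IMP and no later than last dose of IMP+1day will be included". The second is an exclusion rule: "AEs that began prior to the first dose of IMP or more than one day after the final dose of IMP will not be included". Protocol 14.5.1 has only the exclusion rule.

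The dates that feed this window are derived in SAP 14.1. For the start, "The date of first treatment administration will be the day after" the dispensing date at Visit 2. For the end, "The date of last treatment administration will be the day before the date of Visit 3 or Early Termination".

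Two further passages bear on the start of the window. SAP 7.1 states: "Reference start date (Day 0) is defined as the day of randomisation". SAP 7.2 then says that "Adverse Events (AEs) and medications commencing on the reference start date will be considered post-baseline".

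On when treatment begins, protocol 9.5 says the patient "will commence the 7-day treatment period at Visit 2 (Day 0", and protocol 3.7 and SAP 4.1 say the same. Protocol 3.10, 11.3.2.1 and 12.4 have patients start tablets on the day after that visit.

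**The concern.** The inclusion and exclusion sentences should be complements, so that every AE is either in or out. As dates they are not. An AE whose onset date equals the first-dose date is not *after* first dose, so the first sentence leaves it out. It is not *prior to* first dose either, so the second sentence does not remove it. A programmer has to choose, and the word *only* in the first sentence points towards leaving it out.

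The window feeds the trial's safety endpoint. SAP 3.3 assesses safety by the overall proportion of patients with AEs. SAP 16.1.1 compares that proportion, and those for related and severe AEs, by Fisher's exact test. The day at risk is the day of first exposure, when an acute reaction to the tablets could plausibly appear.

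**Working it through.** The plan states no figure to reproduce here. The check has two steps: whether the documents force a date comparison, and how much of the window turns on it.

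**Step 1: can same-day order be established from the listed data?**

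- First dose: SAP 14.1 assigns a date (dispensing plus one day) to every patient and uses no time.
- AE onset: protocol Table 13-1 lists the date the AE started and no onset time.
- Tie-break: SAP 16.1 treats an AE as treatment-emergent when its start date is missing or partial and its status is unclear. A complete date equal to the first-dose date is not covered.
- Contrast: for concomitant medication, SAP 13 writes *on or after* first dose where it means to include that day. SAP 16.1 writes *after*.

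So the comparison has to be made on dates, and the listed fields cannot separate a pre-dose from a post-dose onset on that day.

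**Step 2: window length.** Use the SAP's own derivations, with dispensing on Day 0 and Visit 3 or early termination (ET) on Day V.

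- First-dose date F = 0 + 1 = Day 1.
- Last-dose date L = V − 1.
- Window end = L + 1 = V.
- Onset on or after F: Days 1 to V, which is V days.
- Onset strictly after F: Days 2 to V, which is V − 1 days.
- Share of the window lost under the strict rule = 1/V.

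| Visit | Derived last dose | Window end | On or after F | Strictly after F | Share lost |
|---|---|---|---|---|---|
| ET, Day 1 | Day 0 | Day 1 | 1 day | 0 days | 1/1 = 100% |
| ET, Day 2 | Day 1 | Day 2 | 2 days | 1 day | 1/2 = 50% |
| Visit 3, Day 7 | Day 6 | Day 7 | 7 days | 6 days | 1/7 = 14.3% |
| Visit 3, Day 8 | Day 7 | Day 8 | 8 days | 7 days | 1/8 = 12.5% |
| Visit 3, Day 10 | Day 9 | Day 10 | 10 days | 9 days | 1/10 = 10.0% |

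Protocol Table 11-1 allows early termination from Day 1 to Day 6, so the first row can occur. Under the strict rule, an AE that made a patient stop on the first dosing day would not be counted.

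**Illustration in patients.** The documents give neither an expected AE rate nor an onset pattern, so these inputs are assumptions: 550 per arm (1100/2), one AE per affected patient, Visit 3 on Day 8, uniform onset over Days 1 to 8.

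- True proportion 2%: 550 × 0.02 = 11 patients; 11 × 7/8 = 9.6 counted.
- True proportion 5%: 550 × 0.05 = 27.5; 27.5 × 7/8 = 24.1 counted.
- True proportion 10%: 550 × 0.10 = 55; 55 × 7/8 = 48.1 counted.

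If 30% of onsets fell on Day 1 instead, the 5% case would give 27.5 × 0.70 = 19.3. A patient with a second AE later in the window would still be counted, which makes the loss smaller.

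**The case against.** The strongest reply is that *after first dose* refers to an event in time, not to a calendar date. A reaction to the first tablets begins after them, so it is included, and the two sentences of SAP 16.1 then agree with each other and with protocol 14.5.1. Data capture supports this. Protocol 13.1.2 sends events between consent and IMP administration to medical history, and protocol 13.1.4 records as AEs those arising after administration. If sites follow this, a Day 1 entry on the AE form has already been judged post-dose. This reading is sensible and may be what was meant. It does not settle the programming, because SAP 14.1 supplies only a date and no sentence tells the programmer to keep equal dates.

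The clinical stakes should not be inflated. Protocol section 6 puts allergic manifestations below 1 in 10,000, which for 550 patients on active tablets is fewer than 550/10,000 = 0.055 expected cases.

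A reader might also infer stronger points that the documents do not support:

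- *Day 0 events are promised and then lost as well.* SAP 7.2 defines post-baseline status; it does not decide which events enter the AE summaries. Events before dosing are excluded on purpose.
- *The true first-dose date was never collected.* SAP 14.1 shows which date is used for derivation. The annotated study book cited in SAP 17 is not available here, so non-collection is an inference.
- *The rule tilts the comparison.* It applies identically to both arms.

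**Conclusion.** The point holds as an ambiguity that can produce a wrong count; a loss is possible but not certain. SAP 16.1 can be read to start the window on the derived first-dose date or on the day after it. Under the second reading, first-day onsets leave the AE and SAE summaries and the Fisher tests.

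The difference is one onset day: 1 of 8 with Visit 3 on Day 8, 1 of 7 to 1 of 10 across the permitted visit days, and the entire window for a Day 1 early termination. These are shares of the window. They become shares of events only if onset is uniform, which is an assumption. The effect would be to understate incidence in both arms, with no favour to either by design. Efficacy is untouched, and the reporting of individual SAEs under protocol 13.1.5 does not depend on this window.

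The Day 0 wording in SAP 7.2 is mainly a matter of consistent definitions. It would matter for counts only if a patient took tablets on Day 0, because the derived first-dose date would then be a day late. That is why the passages on the start of treatment need to agree.

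**What to change.** Replace the two sentences in SAP 16.1 with one rule expressed in dates: *AE start date on or after the date of first dose and no later than the date of last dose + 1 day*. State that an onset on the first-dose date counts as treatment-emergent. This errs in the same direction as the SAP's own rule for missing dates.

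Align the Day 0 sentence in SAP 7.2 with that rule, for example by saying that post-baseline status does not by itself place an AE in the summaries.

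Reconcile protocol 3.7 and 9.5 and SAP 4.1 with protocol 3.10, 11.3.2.1 and 12.4 and SAP 14.1 on whether treatment begins on Day 0 or the following day.

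The cost is a change of SAP wording and one comparison operator in the programming. No new data are needed, which matters because SAP 2.0 (29 July 2014) follows the blind data review of 23 July 2014. The downside is that a few events that began on the first dosing day but before the tablets may be counted; protocol 13.1.2 should already have sent most of these to medical history.
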